9. STUDY TREATMENTS AND EXTENT OF EXPOSURE

Study Treatment and extent of exposure summaries will be provided based on the Safety population. Descriptive statistics will be provided by cohort.

9.1. Treatment Duration

Treatment duration in days (calculated as last dose date – first dose date + 1) will be summarized by cohort using the Safety population.

9.2. Treatment Compliance

Treatment compliance is defined as the number of treatments a subject received as a percentage of the number of treatments he or she should have received. Subjects will receive up to 15 injections on Study Days 1 and 8. A subject listing of treatment compliance will be provided by cohort, including any interruptions and/or discontinuation of injections and the reason for discontinuation.

10. EFFICACY ANALYSIS

All efficacy evaluations will be conducted using the EE population.

10.1. Multiplicity

Formal statistical testing will not be performed and interpretation of the statistical significance of results from analyses will not be performed. For this reason, methods to control Type I error for multiple testing are not applicable in this study.

10.2. Analysis of Primary Efficacy Endpoint

The MTD will be reported, including the maximum dose and corresponding incidence of DLT.

10.3. Analyses of Secondary Efficacy Endpoints

The secondary efficacy endpoints will be analyzed based on the EE population.

10.3.1. Secondary Endpoint 1 – ABI and TBI

ABI and TBI will be summarized using descriptive statistics at Screening, on Study Days 1 and 8 prior to administration of IP and on Study Days 15 and 29 and Months 3, 6, 9, 12 and 24. ABI and TBI will be calculated by dividing the systolic blood pressure at the ankle or toe by the systolic blood pressures (Doppler technique) in the arm. Spaghetti plots of ABI and TBI over time will also be provided.

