### **2.2. Secondary Objectives**

The secondary objective is to explore potential clinical efficacy by assessing changes in the ankle-brachial index (ABI) and/or toe brachial index (TBI). Additional assessments will include evaluating changes in Rutherford Criteria; number, extent and size of ulcers; leg rest pain score using a visual analogue scale (VAS); incidence of hospitalization (all cause); overall survival at 24 months; and the time to first occurrence of major amputation (above the ankle) of treated leg, all-cause mortality, doubling of ulcer total surface area from baseline or de novo gangrene.

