### **6.3.3. Ankle-Brachial Index and Toe-Brachial Index**

The ABI and TBI should be obtained bilaterally by measuring both the posterior tibial and dorsalis pedis arteries for the ABI and the first or second toe digital artery for the TBI dividing the systolic blood pressure at the ankle or toe by the systolic blood pressures (Doppler technique) in the arm). ABI and TBI will be assessed during Screening, on Study Days 1 and 8 prior to administration of PDA-002, on Study Days 15 and 29, Months 3, 6, 9, 12, and 24, and at early termination.

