### **7.2. Inclusion Criteria**

Subjects must satisfy the following criteria to be enrolled in the study:

1. Males and females, 18 to 80 years of age at the time of signing the informed consent document.
2. Understand and voluntarily sign an informed consent document prior to any study related assessments/procedures are conducted.
3. Able to adhere to the study visit schedule and other protocol requirements.
4. Diabetes mellitus type 1 or 2.
5. Ischemic or neuro-ischemic diabetic foot ulcer with severity of Grade 1 (full thickness only) or Grade 2 on the Wagner Grading Scale ([Appendix A](#)) of greater than one month duration which has not adequately responded to conventional ulcer therapy.
6. Peripheral arterial disease with ankle-brachial index  $> 0.5$  and  $\leq 0.9$  or toe-brachial index  $> 0.35$  and  $\leq 0.7$ .
7. No planned revascularization or amputation over the next 3 months after Screening visit, in the opinion of the Investigator.
8. Screening should not begin until at least 14 days after a failed reperfusion intervention and at least 30 days after a successful mechanical intervention but longer wait times may be employed at the discretion of the investigator.
9. Subject can have stable angina, (Canadian Cardiovascular Society (CCS) Class I-II angina ([Appendix H](#))).
10. Subjects should be receiving appropriate medical therapy for hypertension and diabetes.
11. A female of childbearing potential must have a negative serum pregnancy test at Screening and a negative urine pregnancy test prior to treatment with study therapy. In addition, sexually active FCBP must agree to use 2 of the following adequate forms of contraception methods simultaneously such as: oral, injectable, or implantable hormonal contraception; tubal ligation; IUD; barrier contraceptive with spermicide or vasectomized partner for the duration of the study and the follow-up period.
12. Males (including those who have had a vasectomy) must agree to use barrier contraception (latex condoms) when engaging in reproductive sexual activity with FCBP for the duration of the study and the follow-up period.

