### **10.6. Efficacy Analysis**

Efficacy analyses will be conducted using the Efficacy Evaluable (EE) population as defined in Section 10.2. Descriptive statistics will be provided primarily for summaries of efficacy endpoints. No formal statistical comparisons are planned due to the small sample size and the exploratory nature of the study.

Descriptive statistics will also be provided for changes in Rutherford Criteria, number, extent and size of ulcers, ABI, TBI, leg rest pain score (VAS), and incidence of hospitalization.

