11.3. Clinical Laboratory Evaluations

The change from baseline in the following laboratory parameters will also be summarized descriptively over time, by cohort and visit:

- a. Serum chemistry, lipid profile, fatty acids, hematology, urinalysis and pregnancy
- b. Coagulation tests
 - Prothrombin time (PT), partial thromboplastin time (PTT), and thrombin activation time (TAT)
 - D-dimers
 - Fibrinogen
 - Tissue factor procoagulant activity (TF-PCA)
 - Platelets
- c. Immunologic/Inflammation Assessments
 - Anti-HLA antibodies
 - C-reactive protein
 - Quantitative assessment of serum immunoglobulins (IgA, IgM, and IgG)
 - Vascular endothelial growth factor (VEGF)
 - Cytokines: interleukin (IL)-1 β , tumor necrosis factor (TNF- α), IL-6, IL-8, IL-10, and transforming growth factor- β (TGF- β)
- d. Tryptase and Histamine
- e. Troponin I
- f. Hemoglobin A1c
- g. Circulating endothelial cells (CECs)

Spaghetti plots of individual lab values and change from baseline values over time will be provided for these lab parameters.

By-subject listings will also be provided for the laboratory data.

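### SAP 10.3.1 summarises ABI and TBI as values per visit, without the change that the objective and Protocol 10.6 call for and without naming leg or cohort

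*SAP*

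**What the plan says.** **Objective and protocol analysis.** Protocol 2.2 and SAP 3.2 both state the secondary objective as exploring efficacy through changes in ABI and/or TBI. Protocol 10.6 carries this into the analysis: "Descriptive statistics will also be provided for changes in Rutherford Criteria, number, extent and size of ulcers, ABI, TBI", followed by leg rest pain and hospitalization.

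**SAP analysis.** SAP 10.3.1 reads "ABI and TBI will be summarized using descriptive statistics at Screening, on Study Days 1 and 8 prior to administration of IP", then continues through Days 15 and 29 to Month 24. It adds "Spaghetti plots of ABI and TBI over time will also be provided". It mentions no change, leg or cohort. Sections 10.3.2 and 10.3.4 to 10.3.6 (ulcer number and size, Wagner grade, Rutherford category, leg rest pain) are by cohort, but they too summarise values per visit only.

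**Measurement.** Protocol 6.3.3 says "The ABI and TBI should be obtained bilaterally by measuring both the posterior tibial and dorsalis pedis arteries for the ABI", with toe pressures for the TBI. Protocol 8.2 puts the injections in one leg.

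**Revascularization.** Inclusion criterion 7 requires "No planned revascularization or amputation over the next 3 months after Screening visit". Protocol 9.2 prohibits nothing afterwards except investigational agents. The readable SAP has no rule for ABI or TBI values obtained after a revascularization.

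**The concern.** There is no control arm, so the basic efficacy readout is how each subject's treated leg moves from its own pre-dose value. SAP 10.3.1 does not ask for that quantity. A programmer following the text would produce a mean and spread of raw indices at each visit. Those means come from whoever attended the visit, and possibly from both legs together.

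Two things then become hard to separate from any effect of the product. First, the set of subjects behind each visit mean can change over 24 months. Second, a revascularization of the treated leg can raise the index directly, and the value would enter the summary unmarked. At 3 to 6 subjects per cohort, either can move a mean noticeably. Because the leg is not fixed in advance, it could also be chosen after the data are seen.

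**Working it through.** **1. Texts side by side.**

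| Item | Protocol | SAP |
|---|---|---|
| Secondary objective | Changes in ABI/TBI (2.2) | Changes in ABI/TBI (3.2) |
| Planned summary | Changes (10.6) | Values per visit and plots (10.3.1) |
| Leg | Both measured (6.3.3), one injected (8.2) | Not named in 10.3.1 |
| Cohort | – | Absent from 10.3.1; present in each of 10.3.2 to 10.3.8 |
| Declared departure | – | None on ABI/TBI in Section 14 |

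The SAP uses both devices elsewhere. For laboratory data it says "The change from baseline in the following laboratory parameters will also be summarized descriptively over time, by cohort and visit", and Sections 11.4 and 11.6 also specify change from baseline for vital signs and ECG. Sections 10.3.3 and 14 restrict amputation, ulcer doubling and gangrene to the treated leg. Their absence from 10.3.1 is therefore not a general style of the document.

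For Rutherford, Protocol 6.3.1 defines improved (at least one category better) and non-responsive. SAP 10.3.5 does not use that classification.

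**2. Figures available.** The documents give no effect size, SD or correlation for ABI or TBI, so there is no figure to reproduce. The only related number is the maximum sample size, 4 cohorts × 6 = 24, which agrees. The values in steps 3, 5 and 6 are assumptions, labelled as such.

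**3. Change in the set of subjects.** Assume a cohort of six with ABI 0.52, 0.60, 0.68, 0.74, 0.82 and 0.90, all inside the range in inclusion criterion 6, and no true change in anyone.
- Mean of all six: 4.26 / 6 = 0.710.
- Without the lowest: 3.74 / 5 = 0.748, a rise of 0.038.
- Without the lowest two: 3.14 / 4 = 0.785, a rise of 0.075.

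The mean within-subject change is 0 in every subset, because each subject's change is 0.

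**4. Weight of one subject.** This is 1/n: 1/6 = 17% and 1/3 = 33% of a cohort mean.

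**5. One revascularized subject.** The shift in the cohort mean is g/n for an ABI gain g. Assume g from 0.15 to 0.30.
- n = 6: 0.15/6 = 0.025 to 0.30/6 = 0.05.
- n = 3: 0.15/3 = 0.05 to 0.30/3 = 0.10.

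**6. What a change summary could show.** The 95% half-width is t(0.975, n−1) × SD/√n.

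| Assumed SD of change | n = 3 | n = 6 | n = 24 |
|---|---|---|---|
| 0.05 | 0.12 | 0.05 | 0.02 |
| 0.10 | 0.25 | 0.10 | 0.04 |
| 0.15 | 0.37 | 0.16 | 0.06 |

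Cohort estimates would be wide. The pooled row of up to 24 is tighter but mixes doses.

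**The case against.** The strongest reply is that this is loose drafting in a descriptive Phase 1 study. The protocol still promises changes, the SAP keeps them in its objective, and nothing withdraws them. With 3 to 6 subjects per cohort, spaghetti plots let a reader follow each trajectory and see who drops out. SAP 10.3.3 also reports times to ulcer doubling and to 50% reduction from baseline, which are within-subject changes. SAP 5.1 and parts of the date-handling appendix are blacked out and the Table of Events is not shown, so a baseline definition may exist.

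Much of that stands, and it rules out several stronger readings that a reader might infer:

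- *That within-subject change is nowhere reported.* The plots and 10.3.3 show some of it. What is missing is a summary of change for ABI/TBI and for the endpoints in 10.3.2 and 10.3.4 to 10.3.6.
- *That the untreated leg is a wasted concurrent control.* It need not have PAD, and with bilateral ulcers the leg with the larger ulcer area is the one treated (Protocol 4.1). Subtracting the legs does not cancel arm pressure: A/P − B/P = (A − B)/P still has the arm pressure P in the denominator. With equal variances, the SE of the between-leg difference in change relative to treated-leg change alone is √(2(1−ρ)): 1.41 at ρ = 0, 1.00 at ρ = 0.5 and 0.71 at ρ = 0.75. Precision improves only if the between-leg correlation of changes exceeds 0.5, and the documents give no such figure.
- *That the plan loses a stated amount of precision against paired analysis.* That would compare with treating visits as independent samples, which the SAP does not plan.
- *That a revascularization would be counted as a response to the product.* No ABI/TBI response is defined, and therapies and procedures are recorded. The values can be identified; the SAP just does not say to do so.
- *That the efficacy data become uninterpretable, or that they are what sets Phase 2.* Protocol 4.2 gives that role to the MTD and says the numbers are inadequate to determine benefit unless responses are dramatic.

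What does not stand is that the plots suffice. They show raw values with no leg named and give no summary of the quantity in the objective. A baseline definition in redacted text would not by itself add a change analysis to 10.3.1.

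**Conclusion.** The point holds as an undeclared departure of the SAP from the protocol on a secondary endpoint. SAP 10.3.1 omits the change summary and leaves leg and cohort open; 10.3.2 and 10.3.4 to 10.3.6 share the lack of a change summary. This rests on the readable text and needs no assumption.

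The sizes are illustrative. The 17% to 33% weight follows from the cohort sizes alone. The 0.038 and 0.075 shifts depend on the assumed ABI values and on who is lost. The 0.025 to 0.10 shift depends on an assumed gain, and the documents give no revascularization rate. Within-subject change removes the effect of a changing set of subjects on baseline level, but not bias from drop-out that is itself related to change.

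The MTD and the safety analyses are unaffected. The correction should be made before database lock.

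**What to change.** In SAP 10.3.1:

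- Report the observed value and the within-subject change from the Day 1 pre-dose value for the treated leg, by cohort and visit and pooled, in subjects with both values, showing n. Day 1 is preferable to Screening as the reference because Screening is when eligibility on ABI or TBI is assessed.
- Show the untreated leg alongside as descriptive context only, without presenting it as a control or as a correction for arm pressure.
- Flag values after treated-leg revascularization or amputation and give the summaries with and without them. Both are needed, because excluding such values also removes subjects selectively.

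Add change from Day 1 to 10.3.2 and 10.3.4 to 10.3.6, and tabulate the improved/non-responsive classification from Protocol 6.3.1 in 10.3.5. If the sponsor prefers values per visit only, SAP 14 should state and justify that departure.

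The cost is SAP wording and a few more tables. Bilateral ABI/TBI, procedures and amputation status are already collected. The downside is wide descriptive estimates at 3 to 6 subjects, which should be presented as such.

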10.3.2. Secondary Endpoint 2 – Number of Ulcers and Size of Index Ulcer

The number of ulcers (total on both legs) and the size of the index ulcer (length, width, and depth, and area with the EZ Graph measures) will be summarized separately by cohort at Screening and again on Study Days 1, 8, 15, and 29 and Months 3, 6, 9, 12, and 24. Spaghetti plots of ulcer area, length, width, and depth over time will also be provided.

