### 3.2. Secondary Endpoints

The secondary endpoints are to explore clinical efficacy and include:

1. ABI and TBI will be calculated by dividing the systolic blood pressure at the ankle or toe by the systolic blood pressures (Doppler technique) in the arm. ABI and TBI will be measured during Screening, on Study Days 1 and 8 prior to administration of IP and on Study Days 15 and 29 and Months 3, 6, 9, 12 and 24.
2. The number, extent, and size of ulcers (summation of the products of the long x short axis for all ulcers measured in centimeters squared, plus ulcer depth) will be evaluated and photographs of ulcers taken during Screening and again on Study Days 1, 8, 15, and 29 and Months 3, 6, 9, 12, and 24 ([Appendix E](#), [Appendix F](#)).
3. Time to major amputation (above the ankle) of treated leg, doubling of ulcer total surface area from baseline and de novo gangrene.
4. Wagner Grading Scale ([Appendix A](#)) assessed during Screening and on Study Days 1, 8, 15, and 29 and Months 3, 6, 9, 12, and 24.
5. Rutherford Criteria ([Appendix B](#)) assessed during Screening and on Study Days 1, 8, 15, and 29 and Months 3, 6, 9, 12, and 24.
6. Leg rest pain score - visual analogue scale (VAS) ([Appendix D](#)) graded from 0 (pain free) to Grade 10 (maximum pain) during Screening, on Study Days 1 and 8 prior to administration of PDA-002 and on Study Days 15 and 29 and Months 3, 6, 9, 12, and 24.
7. Overall survival at 24 months (time from PDA-002 administration to any cause of death, subjects still alive will be censored at the date of last follow-up).
8. Incidence of hospitalization (all cause).

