Subjects will undergo screening evaluations to determine eligibility within 28 days of Study Day 1. Following Screening, subjects will be assigned to the appropriate cohort as outlined above and will receive IP. In the case of bilateral limb ulcers, the treated limb will be the limb that has the largest ulcer total surface area. During the treatment period, subjects will receive intramuscular (IM) injections of PDA-002 on Study Days 1 and 8. No more than 1 subject may begin treatment in any 48-hour period. During the follow-up period subjects will be evaluated on Study Days 15 and 29, and Months 3, 6, 9, 12, and 24. All subjects are to receive standard of care treatment in addition to IP. An interim analysis will be performed after the last subject completes 3 months of follow-up.

All subjects who receive any dose of PDA-002 will participate in the 24-month follow-up period. Refer to [Figure 2](#) in this section for the overall study visit design and Section 5, [Table 2](#), Table of Events for the scheduled visits and assessments.

Primary safety assessments, including AE reporting, physical examinations, vital sign measurements, ECG, injection site assessments, MRI or CT scan results, retinal examination results, concomitant medications, and clinical laboratory evaluations will be performed at scheduled visits throughout the study.

Efficacy analyses will include assessment of changes in the ABI and/or TBI. Additional assessments include evaluation of changes in Rutherford Criteria, number; extent and size of ulcers; leg rest pain score using a VAS, incidence of hospitalization (all cause); overall survival at 24 months; and the time to first occurrence of major amputation (above the ankle) of treated leg, all-cause mortality, doubling of ulcer total surface area from baseline, or de novo gangrene (see Section 3).

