### **6.3.2. Ulcer Assessment**

Ulcers will be graded using the Wagner Grading Scale ([Appendix A](#)) and will also be assessed using the E-Z graph system [Appendix E](#)). In addition, photographs will be taken of the ulcers

(Appendix F). The number, extent, and size of ulcers, including summation of the products of the long x short axis for all ulcers measured in centimeters squared plus the ulcer depth will be captured. Ulcer healing is defined as skin closure without drainage or need for dressing. Limbs will also be assessed for gangrene. Ulcers will be assessed at Screening, on Study Days 1, 8, 15, and 29, Months 3, 6, 9, 12, and 24, and at early termination. Information for ulcers assessed at non-scheduled visits will also be collected.

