4.2.2. Secondary Efficacy Endpoints

The secondary endpoints are to explore clinical efficacy and include:

- 1) ABI and TBI will be calculated by dividing the systolic blood pressure at the ankle or toe by the systolic blood pressures (Doppler technique) in the arm. ABI and TBI will be measured during Screening, on Study Days 1 and 8 prior to administration of IP and on Study Days 15 and 29 and Months 3, 6, 9, 12 and 24.

- 2) The number of ulcers and the size of the index ulcer (length, width, depth and EZ Graph area) will be evaluated and photographs of ulcers taken during Screening and again on Study Days 1, 8, 15, and 29 and Months 3, 6, 9, 12, and 24 (Appendix E, Appendix F of study protocol).
- 3) Time to major amputation (above the ankle) of treated leg, doubling of index ulcer total surface area from baseline, de novo gangrene of treated leg, reopening of closed ulcer, index ulcer reduction by 50%, and time to ulcer healing. Number of ulcers that completely close at 3 months, if they closed at least 50% at one month.
- 4) Extent of ulcers will be examined with the Wagner Grading Scale. The Wagner Grading Scale (Section 16.3) is assessed during Screening and on Study Days 1, 8, 15, and 29 and Months 3, 6, 9, 12, and 24.
- 5) Rutherford Criteria (Section 16.4) assessed during Screening and on Study Days 1, 8, 15, and 29 and Months 3, 6, 9, 12, and 24.
- 6) Leg rest pain score - visual analogue scale (VAS) (Appendix D of study protocol) graded from 0 (pain free) to Grade 10 (maximum pain) during Screening, on Study Days 1 and 8 prior to administration of PDA-002 and on Study Days 15 and 29 and Months 3, 6, 9, 12, and 24.
- 7) Overall survival at 24 months (time from PDA-002 administration to any cause of death, subjects still alive will be censored at the date of last follow-up).
- 8) Incidence of hospitalization (all cause).

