14. CHANGES TO THE STATISTICAL ANALYSES SECTION OF THE PROTOCOL

The analysis of secondary endpoints of De Novo gangrene and doubling of index ulcer (Section 10.3.3) will be restricted to the treated leg only.

The time to event analysis of re-opening of closed ulcer, time to index ulcer reduction by 50% and time to ulcer healing described in Section 4.2.2 and 10.3.3 are additional analysis to that described in the protocol.

Urinary cotinine is listed in Section 3.1 of the protocol as a primary endpoint. The test is a measure of nicotine use. Since the protocol was amended to include smokers, it is not necessary to track nicotine use in patients and, therefore, an analysis of urinary cotinine values will not be performed..

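### The SAP replaces the protocol's all-ulcer area with one undefined index ulcer without declaring it, and adds a closure count limited to early responders with no denominator or analysis

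*SAP*

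**What the plan says.** **Protocol.** Endpoint 2 in Section 3.2 defines ulcer size as "summation of the products of the long x short axis for all ulcers measured in centimeters squared, plus ulcer depth". Section 6.3.2 makes this a data-capture requirement: "The number, extent, and size of ulcers, including summation of the products of the long x short axis for all ulcers". Endpoint 3 in Section 3.2 includes, after major amputation, "doubling of ulcer total surface area from baseline and de novo gangrene". Healing carries no condition on early response: "Ulcer healing is defined as skin closure without drainage or need for dressing". The readable protocol text does not use the term index ulcer.

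**SAP.** Section 10.3.2 summarises "The number of ulcers (total on both legs) and the size of the index ulcer", the latter by length, width, depth and E-Z Graph area. Section 4.2.2 lists the same measures. Section 10.3.3 applies doubling (in the treated leg) and a new 50% reduction event to the index ulcer, and Section 3.2 rewords the secondary objective to match. Endpoint 3 in Section 4.2.2 also adds "Number of ulcers that completely close at 3 months, if they closed at least 50% at one month".

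**Declared changes.** SAP Section 14 says that "The analysis of secondary endpoints of De Novo gangrene and doubling of index ulcer" will be limited to the treated leg. It names three added time-to-event analyses (reopening, 50% reduction, healing) and drops urinary cotinine. It lists nothing else.

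**The concern.** The SAP as written never produces the protocol's area endpoint or its doubling event. Section 14 speaks of doubling of the index ulcer as if the protocol had already defined it that way, so a reader relying on that section would not learn that the measure has changed.

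The change matters only for subjects with several ulcers, but the design expects some: "In the case of bilateral limb ulcers, the treated limb will be the limb that has the largest ulcer total surface area" (Protocol Section 4.1). In such subjects the leg is chosen on total area and its change in size is then judged on one ulcer. Because the study is open-label and no readable rule fixes which ulcer is the index or when, the choice could be made after responses are visible.

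The closure count is a separate problem. It selects ulcers on a response seen after treatment, and its meaning depends on a denominator that the SAP does not give.

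**Working it through.** The plan states no figure to reproduce here: there is no hypothesis test, power or target effect for these endpoints. The check compares the definitions and then asks when they disagree. All areas and counts below are assumed for illustration.

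**1. Definitions side by side**

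| Item | Protocol 3.2, 6.3.2 | SAP 4.2.2, 10.3.2, 10.3.3 | Declared in SAP 14? |
|---|---|---|---|
| Size | Sum of axis products, all ulcers, plus depth | Length, width, depth, E-Z Graph area of index ulcer | No |
| Doubling | Total ulcer area | Index ulcer area, treated leg | Leg restriction only |
| 50% reduction | None | Index ulcer area | Yes, as an addition |
| Month 3 closure if ≥50% closed at one month | None | In 4.2.2; no analysis in 10.3 | No |

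**2. SAP favourable event with protocol adverse event**

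Index ulcer 4 → 2 cm², other ulcer 3 → 12 cm².
- Index ratio: 2/4 = 0.5, which is the SAP's 50% reduction.
- Total: 4 + 3 = 7 and 2 + 12 = 14; 14/7 = 2.0, which is the protocol's doubling.

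In general, let f be the index ulcer's share of baseline total area. If the index ulcer halves, the total doubles when the other ulcers grow by a factor g, where 0.5f + (1 − f)g = 2. So g = (2 − 0.5f)/(1 − f).
- f = 25%: g = 1.875/0.75 = 2.5
- f = 50%: g = 1.75/0.50 = 3.5
- f = 75%: g = 1.625/0.25 = 6.5

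In the example f = 4/7 and g = 12/3 = 4.

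**3. The reverse**

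Index ulcer 2 → 4 cm², with 4 cm² elsewhere unchanged.
- Index ratio: 4/2 = 2.0, a SAP doubling.
- Total ratio: (4 + 4)/(2 + 4) = 8/6 = 1.33, not a protocol doubling.

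**4. What each measure misses**

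Growth of an existing non-index ulcer enters no SAP area endpoint. A new ulcer does enter the SAP's ulcer count. With a single ulcer, both measures follow the same ulcer.

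**5. Closure count**

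Take 10 ulcers. Five reach 50% closure at one month, and 4 of these close by Month 3. Five do not, and 1 of these closes.
- All closures: (4 + 1)/10 = 50%.
- SAP count: 4.
- As a rate: 4/10 = 40% over all ulcers, or 4/5 = 80% over early responders. The SAP does not say which, or whether a rate is meant.

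**The case against.** The strongest reply is that these are exploratory, descriptive summaries. Protocol Section 10.6 plans no formal comparisons, and Protocol Section 4.2 concedes that the study is too small to show benefit unless responses are dramatic. Limb worsening is also picked up elsewhere: Wagner grade, Rutherford category, de novo gangrene, major amputation and adverse events. Time to healing has no early-response condition, so later closers are not lost. An index-ulcer definition might sit in redacted or missing text (SAP Section 5.1, the protocol's Table 2, Appendix F). All of this stands, and it limits the weight of the point. None of it supplies the protocol's total-area result or declares its replacement.

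A reader might infer more than the documents support:
- **That the choices systematically favour the product.** Step 3 shows that the index switch can also count against it. The closure count drops late closers from its numerator, and it raises a rate only if early responders form the denominator.
- **That new ulcers on the injected leg are ignored.** Section 10.3.2 counts them at every visit.
- **That counting ulcers on both legs departs from the protocol.** The protocol refers to all ulcers and names no leg for this endpoint.
- **That the SAP uniquely lets amputation improve the result.** Removing an ulcer-bearing part lowers the protocol's number and total area as well.
- **That a subject is a success under one document and a failure under the other.** Neither document defines ulcer success or failure for a subject.

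**Conclusion.** The point holds in this form. The SAP substitutes a single index ulcer, undefined in any readable text, for the protocol's total ulcer area. Section 14 does not declare the substitution, so the protocol's area and doubling endpoints go unreported. The SAP also adds a closure count that is conditioned on post-treatment response, with no denominator, analysis or declaration.

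The size is moderate. Disagreement needs more than one ulcer. For the total to double while the index ulcer halves, the other ulcers must grow 2.5-fold to 6.5-fold for index shares of 25% to 75%. The documents do not say how many subjects have several ulcers, so no frequency can be given, and the direction is not fixed. The endpoints are secondary and descriptive, and determination of the MTD is untouched. The sponsor should correct this before database lock, but it does not threaten the study's primary purpose.

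**What to change.** Amend the SAP as follows.
- **Sections 4.2.2, 10.3.2 and 10.3.3:** report the protocol's total ulcer area, for all ulcers and for the treated leg, with its change from baseline and time to its doubling. Show these beside the index-ulcer results.
- **Index ulcer:** state a baseline rule that identifies it and fixes it before dosing.
- **Closure:** report Month 3 closure over all baseline ulcers. Show the subset at least 50% closed at one month as a separate row with its own denominator, and add the analysis to Section 10.3.
- **Section 14:** list the move from total area to index ulcer, and the closure count.

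The cost is SAP wording and a few more descriptive tables. Protocol Section 6.3.2 already requires the all-ulcer measurements, so no new data are needed if the case report form follows it. The downside for the sponsor is that results may look less favourable. Per-leg ulcer counts, special scoring of amputated ulcers, or reducing the index ulcer to a supportive role are matters of preference and are not needed to correct the defect.
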